1.2 Research Fellow and Deputy to [name]

Dr. med. [name], Physician/Fellow, Clinic for Anaesthesiology, Center for Anaesthesiology and Intensive Care, University Hospital Hamburg-Eppendorf, Germany

2. Table of Abbreviations

ANOVA	analysis of variance
ASA	American Society of Anesthesiology
BNP	brain natriuretic peptide
CPR	cardiopulmonal resuscitation
CRP	C-reaktive protein
ECMO	extracorporal membrane oxygenation
GOT	Glutamate-Oxalacetate-Transaminase
GPT	Glutamate-Pyruvate-Transaminase
HR	heart rate
IL	Interleukin
MAP	mean arterial pressure
NSE	neuron-specific enolase
РСТ	Procalcitonin
S1P	Sphingosin-1-Phosphate
TNF	tumor necrosis factor
CVP	central venous pressure

3. Purpose of the Study

A cardiac arrest with subsequent cardiopulmonary resuscitation (CPR) is even in case of a successful return of spontaneous circulation regularly associated with critical ischemia of body tissue. Together with damage caused by reperfusion, this is causing a systemic inflammatory reaction with release of cascades of pro- and antiinflammatory cytokines, taking part in impairing the clinical outcome of the patient.

Yet, for many patients it is even impossible to reconstitute a proper spontaneous circulation in the course of a mechanical and pharmaceutical CPR. Nowadays some of those, under certain circumstances, might be available for temporary support by veno-arterial extracorporal membrane oxygenation (va-ECMO)

To establish this device, a physican is installing central venous and arterial intravascular catheters during the course of the CPR. Those are then connected to an external system consisting of a pumping unit and a membrane for gas exchange, the oxygenator. This veno-arterial ECMO thus constitutes a modified version of a heart-lung-machine and is capable of performing a temporal and partial cardio-pulmonary bypass, relieving stressed heart and lung of the patient from a certain workload. The system's maintenance is performed by specifically trained physicians and technicians. It's modular concept allows for the exchange of certain parts with only minor or even entirely without interruptions in therapy. Thus, the additional implementation of a adsorber module as performed in this study, does not constitute a relevant threat to patient safety and survival.

As mentioned above, the concept of va-ECMO in resuscitated patients is to disburden vital organs in a critical phase and thus to facilitate their recovery under supportive intensive care and/or to get time to initiate further procedures in order to eliminate the original cause for cardiopulmonary arrest.

In this study, we aim to show, whether patients after CPR with subsequent va-ECMO profit from an additional modulation of the inflammatory reaction via hemoadsorption (Cytosorb®) in terms of levels of inflammatory cytokines and ultimaltely in organ function and survival.

4. Prior Knowledge

Patients with cardiopulmonary arrest and subsequent CPR are regularly harmed by a subsequent systemic inflammatory reaction with many parallels to those suffering from sepsis. In both groups, there is a significant increase in the levels of pro-inflammatory cytokines as interleukin 6 (IL-6). According to present data, there seems to be a positive correlation between the individual level of this increase and terminal mortality of the patients (1).

With hemoadsorption (Cytosorb®, MedaSorb Technologies, Princeton, N.J., USA), a device for effective elimination of cytokines like tumor necrosis factor α (TNF- α), interleukine 6 (IL-6) and 8 (IL-8) from the patient's bloodstream is available. This device is CE-certified for a use in extracorporal circulation and has been in clinical use worldwide for successful adsorbtion of cytokines, yet as to our knowledge never for routine elimination of circulating cytokines in a post-resuscitation setting so far.

Previous studies were able to establish the capability of the Cytosorb adsorber to eliminate IL-6, interleukine 10 and TNF- α from the serum and reduce the mortality under severe sepsis in an animal model (2).

As for the clinical application in humans, there are several case reports attributing a positive outcome for severely affected patients to the use of hemoadsorption. A significant reduction of cytokines by the device has been shown in patients under sepsis (4), systemic inflammation caused by sepsis (5) and systemic inflammation without sepsis (6) (own publication, *submitted*).

As to our knowledge, there is currently no data available for the application of this device in severe systemic inflammation after cardiac arrest, CPR or va-ECMO subsequent to the named conditions.

5. Study Conception and Project Outline

5.1 primary and secondary endpoints

In this study, we aim to show that hemoadsorption (Cytosorb®) is a viable option to reduce serum levels of proinflammatory cytokines in patients under va-ECMO after CPR. Specifically, our hypothesis constitutes significantly lower levels of IL-6 and TNF- α in patients undergoing hemoadsorption for 48 hours compared to a control group receiving standard medical care at va-ECMO during a 72 hours-timeframe.

Primary outcome parameters

Laboratory parameters expressing an inflammatory response constitute the primary outcome of our study. Thus,

IL-6, TNF-a, S1P, PCT, CRP, leucozytes

are to be measured at time points 0,6,12,24,48 and 72 hours after administration to va-ECMO.

Secondary outcome parameters

Those are supposed to reflect secondary and tertiary effects of the hemoadsorption on organ function and overall survival of the patients:

- 1. Laboratory and clinical parameters of inflammation and organ damage/dysfunction (cardiovasculary, pulmonary, hepatic, renal, neuronal):
 - NSE, (free) hemoglobine, haptoglobine, BNP, Troponine, Creatinekinase, Myoglobin, GOT, GPT, Creatinine
 - cardiovasculary: (MAP, CVP, HR,. echocardiographic parameters)
 - pulmonary: oxygenation/decarboxylation, acid-base-balance by blood gas analysis

- 2. Parameters of treatment:
 - Cardiovasculary: Dependence on inotropics, and vasopressors, volume substitution or elimination,
 - pulmonary: relevant parameters of ventilation
 - additional organ replacement therapy (dialysis, hepatic replacement)
- 3. Parameters of terminal outcome
 - mortality within the first 30 days after inclusion into the study
 - length of stay in intensive care/in hospital

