5.3 Sample size

We expect a difference of 20-30% in serum concentration of IL-6 at 24 hours after inclusion (about 60µg/L difference at total levels of 200-300µg/L, standard deviation 90µg/L). With 18 patients per group, the study could determine a significant difference between the groups with a power of 90% and an error propability of 5% by ANOVA. To attribute for post-hoc exclusion or drop-out of participants with an estimated rate of 10%, we suggest a sample size of 20 patients per group, adding to a total of 40 participants in the study

This calculation is based on the publication of Adrie C. Et al. (1) and on a previous study performed in our department (publication pending).

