5.6 Randomization

Randomization is performed at the time of establishment of va-ECMO. Drawing without returning of prepared sealed envelopes will ensure an identical size of 20 participants each for control and intervention groups .

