5.7. Statistical analysis

Statistical analysis is conducted using the software package SPSS. To characterize the patients, we are going to conduct descriptive analytics in dependence on the statistical distribution of variables.

Continuous variables like hemodynamic and laboratory parameters are analyzed using a multifactorial ANOVA or a mixed lineary model.

Nominal or categorized variables are going to be analyzed in four-to-multi-square-tables with chi-square-tests or Fisher's exact test.

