5.8. Time points and parameters

Time points:

- 1) on administration to va-ECMO
- 2) 6 hours post administration to va-ECMO
- 3) 12 hours post administration to va-ECMO
- 4) 24 hours post administration to va-ECMO
- 5) 48 hours post administration to va-ECMO
- 6) 72 hours post administration to va-ECMO

Parameters

- 1. inflammatory:
 - IL-6
 - TNFα
 - S1P
 - PCT
 - CRP
 - leukozytes
- 2. cardiocirculatory
 - MAP, CVP, HR
 - Dependence on external inotropes or vasopressors
 - BNP, Troponine, Creatinekinase, Myoglobine, Haptoglobine
 - echocardiographic parameters
- 3. gas exchange in arterial blood gas analysis
 - partial pressures of Oxygen and Carbon dioxide
 - pH and lactate
 - Base excess
- 4. hepatic
 - GOT, GPT
- 5. renal
 - diuresis
 - fluid balance
 - serum creatinine
 - glomerularic filtration rate estimated by CKD-EPI-formula

Additionally, we are going to evaluate demographic data (functional status in accordance with ASA-classification, age, sex, size, total body weight) and periprocedural parameters with specific focus on CPR (duration/time prior to va-ECMO, cause of arrest).

Overview of the study

Principal investigator	[name]. [name]
Title	HaemoAdsorption Nach Reanimation An ECMO (HANRAE)
Hypothesis	Additional hemoadsorption (Cytosorb®) in the extracorporal
	circulation established by va-ECMO in patients after cardiac arrest
	and CPR reduces the levels of IL-6 and TNF α in the serum.
Target population	Patients under va-ECMO subsequent to cardiac arrest and CPR
Primary endpoints	Levels of IL-6 und TNF α in the patients' serum in an interval of 72
	hours post resuscitation
Secondary endpoints	• Laboratory and clinical parameters of inflammation and
	organ damage/dystunction (cardiovascular, pulmonary,
	 Parameters of intensive care treatment (e.g. ventilation)
	additional organ replacement therapy)
	 Parameters of terminal outcome (mortality)
study design	single-centerd prospective controlled randomized
inclusion criteria	 Age ≥ 18 years
	cardiac arrest with CPR
	application of va-ECMO for insufficient spontaneous
	circulation
exclusion criteria	contraindication for va-ECMO in accordance with the
exclusion cinteria	standard operating procedures of the University Cardiac
	Arrest Center Hamburg ECMO bei Reanimation – see 5.4
	for details
sample size	We expect a difference of 20-30% in serum concentration of IL-6
	at 24 hours after inclusion (about 60µg/L difference at total levels

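### The 0 h sample, effectively a baseline, is listed as a primary outcome measurement, and no primary contrast ties the 72 h comparison to the 24 h basis of the sample size

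*Protocol*

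**What the plan says.** - **Hypothesis (Section 5.1).** IL-6 and TNF-α are expected to be lower "in patients undergoing hemoadsorption for 48 hours compared to a control group receiving standard medical care at va-ECMO during a 72 hours-timeframe". The Overview of the study likewise gives the primary endpoint as levels "in the patients' serum in an interval of 72" hours.
- **Outcome samples (Section 5.1).** The primary laboratory parameters "are to be measured at time points 0,6,12,24,48 and 72 hours after administration to va-ECMO". The 0 h sample is on the same footing as the others.
- **Timing of the first sample (Sections 5.6 and 5.8).** Time point 1 is "on administration to va-ECMO", and "Randomization is performed at the time of establishment of va-ECMO".
- **Sample size (Section 5.3).** "We expect a difference of 20-30% in serum concentration of IL-6 at 24 hours after inclusion", quantified as "about 60µg/L difference at total levels of 200-300µg/L" with SD 90 µg/L. It gives 18 evaluable patients per group, raised to 20 for drop-out.
- **Analysis (Section 5.7, Statistical analysis).** "Continuous variables like hemodynamic and laboratory parameters are analyzed using a multifactorial ANOVA or a mixed lineary model". No contrast, time point or role for the 0 h value is given.

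**The concern.** Three time frames stand side by side: 48 h of adsorption, a 72 h comparison, and a sample size set at 24 h. The 0 h sample coincides with randomisation, so the device cannot yet have had an appreciable effect on it. Treated as an outcome, it contributes an expected group difference of zero. If adsorption starts near 0 h, the 72 h sample falls about 24 h after adsorption ends and may show less than the full effect.

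If all six samples enter one group effect, the tested difference is smaller than the 60 µg/L used in Section 5.3. A device that lowers cytokines while connected could then be reported as having no significant effect. The 0 h value would also be used as an outcome carrying no treatment information, when as a covariate it would remove between-patient variation.

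**Working it through.** **Inputs from the protocol.** Difference 60 µg/L, SD 90 µg/L, 18 evaluable per group, 5% error (taken as two-sided, as an ANOVA F-test implies), six sampling times.

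**Assumptions, not in the protocol.** SD 90 µg/L at every time; equal correlation ρ between any two times, shown at 0.3, 0.5 and 0.7; true difference 0 at 0 h and 60 at 6, 12, 24 and 48 h; at 72 h either 0 (effect gone) or 60 (effect persists).

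**Step 1: the plan's own figure.** For a single comparison at 24 h the standard error is 90 × √(2/18) = 30, so the noncentrality is 60/30 = 2.0. Noncentral-t power is 49%, and 90% power needs 49 per group. The stated 18 is not reproduced. This is a separate issue from the present point, but it means the benchmark at 24 h is 49%, not 90%.

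**Step 2: one group effect over six samples.**
- Average difference, effect gone at 72 h: (0 + 4 × 60 + 0)/6 = 40, a loss of 33%.
- Average difference, effect persists at 72 h: (0 + 4 × 60 + 60)/6 = 50, a loss of 17%.
- SD of a patient's six-sample mean: 90 × √((1 + 5ρ)/6), which is 58.1, 68.7 and 77.9 at ρ = 0.3, 0.5 and 0.7.

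**Step 3: 0 h as covariate, mean of the five later samples.**
- Average difference, effect gone at 72 h: (4 × 60 + 0)/5 = 48. Effect persists: 60.
- The five-sample mean has variance 90² × (1 + 4ρ)/5 and covariance 90² × ρ with the 0 h value. The residual SD is therefore 90 × √((1 + 4ρ)/5 − ρ²), which is 53.2, 53.2 and 46.8. The first two agree because the bracket equals 0.35 at both ρ = 0.3 and ρ = 0.5.

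**Power with 18 per group** (standard error = SD × √(2/18) = SD/3). The lower figure in each range is for no effect at 72 h, the upper for full persistence.

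| ρ | Six-sample group effect | Five later samples, adjusted for 0 h |
|---|---|---|
| 0.3 | 52–71% | 75–91% |
| 0.5 | 40–56% | 75–91% |
| 0.7 | 32–46% | 85–96% |

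At ρ = 0.5, for example, the six-sample standard error is 68.7/3 = 22.9, with noncentrality 40/22.9 = 1.75 or 50/22.9 = 2.18. The adjusted analysis has standard error 53.2/3 = 17.7, with noncentrality 48/17.7 = 2.70 or 60/17.7 = 3.38.

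**Step 4: other tests that the text allows.**
- 24 h alone, adjusted for 0 h, has SD 90 × √(1 − ρ²): power 53%, 61% and 78% at ρ = 0.3, 0.5 and 0.7.
- Group-by-time interaction (F with 5 and 170 df): 34–53%, 46–69% and 71–91%. Here the lower figure is for persistence at 72 h and the upper for no effect at 72 h.

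**The case against.** The strongest objection is that no dilution is written into the protocol. A reader might infer from the 72 h wording that the 0 h and 72 h samples necessarily weaken the primary test. The documents do not support that. Section 5.7 names two model families and no contrast. A 24 h contrast, a group-by-time test or a model with 0 h as covariate fits the same text, and a zero difference at 0 h dilutes none of them. This stands, so the loss is conditional on a single group effect over all six samples. The interaction can even have higher power at high correlation, although a significant result would show that profiles differ, not that levels are lower.

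A second tempting reading is that the window ought to stop at 48 h. That would change the stated question from reduction through 72 h to removal while connected. The protocol does not say when the adsorber starts relative to 0 h, and nothing in it shows that the effect is lost by 72 h. This also stands: the window is a trade-off for the sponsor. Nor is moving to 24 h alone a sure gain, since its unadjusted power of 49% is below the 52–71% of the six-sample effect at ρ = 0.3.

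Finally, contrasts and baseline handling are often left to an analysis plan, which may exist. That excuses the missing detail. It does not remove what the protocol itself states: 0 h is listed as a primary outcome measurement, and the comparison window differs from the time point that was sized.

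**Conclusion.** The point holds in a conditional form. What the document establishes is that a sample taken at randomisation is listed among the primary outcome measurements, and that a 72 h comparison is paired with a 24 h sample size without a contrast linking them. If all six samples enter one group effect, the expected difference falls by 17–33%, and power at ρ = 0.3 to 0.7 lies between 32% and 71%. Entering 0 h as a covariate for the five later samples instead gives about 75–96% over the same range.

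The sizes rest on a flat 60 µg/L effect from 6 to 48 h, a constant SD and equal correlation. Section 5.3 supports the 60 and the 90 µg/L for IL-6 at 24 h only, and gives no figures for TNF-α. The advantage of the baseline-adjusted analysis over the six-sample effect holds at each correlation shown.

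**What to change.** 1. In Sections 5.1 and 5.7 (Statistical analysis), remove 0 h from the outcome time points and enter it as a baseline covariate in the mixed model for the 6 to 72 h samples.
2. Name the primary contrast, either the post-baseline mean or the 24 h value, and make Section 5.3 rest on the same one.
3. Report the 72 h group contrast separately as well, so that persistence after adsorption can be seen whichever primary contrast is chosen. The sponsor should state and justify whether the primary window ends at 48 h or 72 h.

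The cost is a few sentences in the protocol or analysis plan, fixed before outcome data are examined. It needs no new samples or patients. The sample-size figure in Section 5.3 needs its own correction, which this change does not replace.

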	of 200-300µg/L, standard deviation 90µg/L). With 18 patients per
	group, the study could determine a significant difference between
	the groups with a power of 90% and an error of propability of 5%
	by ANOVA.
	To attribute for post-hoc exclusion or drop-out of participants, we
	suggest a sample size of 20 patients per group, adding to a total of
	40 participants in the study.
randomization	Randomization is performed as drawing without returning to
	ensure an identical size for control and intervention groups

Hamburg, 29.12.2017

6. Literature

6. Bernardi MH, Rinoesl H, Dragosits K, Ristl R, Hoffelner F, Opfermann P, et al. Effect of hemoadsorption during cardiopulmonary bypass surgery - a blinded, randomized, controlled pilot study using a novel adsorbent. Critical care. S016;20:96.

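### Section 5.1 makes six inflammatory markers primary, while the hypothesis and the Overview make only IL-6 and TNF-α primary

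*Protocol*

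**What the plan says.** The Protocol states its primary outcome in several places.

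- Section 5.1, under the primary-outcome heading: "Laboratory parameters expressing an inflammatory response constitute the primary outcome of our study". The list that follows is "IL-6, TNF-a, S1P, PCT, CRP, leucozytes", measured at 0, 6, 12, 24, 48 and 72 hours.
- Section 5.1, opening paragraph: "our hypothesis constitutes significantly lower levels of IL-6 and TNF- α in patients undergoing hemoadsorption for 48 hours", compared with standard care over 72 hours.
- Overview of the study, hypothesis row: additional hemoadsorption after cardiac arrest and "CPR reduces the levels of IL-6 and TNF α in the serum".
- Overview of the study, primary-endpoints row: "Levels of IL-6 und TNF α in the patients' serum in an interval of 72" hours.

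Three other places bear on the point without settling it:

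- Section 5.3, repeated in the Overview's sample-size row, sizes the trial on "serum concentration of IL-6 at 24 hours after inclusion" with one 5% error probability.
- Section 5.8 groups the same six markers as inflammatory and gives none of them a primary label.
- Section 5.7 (statistical analysis) covers continuous variables in general and names no deciding marker.

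**The concern.** The primary outcome should be the same wherever the protocol states it. Here two lists of different length both carry the primary label. S1P, PCT, CRP and leucocytes are on one and not on the other.

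The practical risk arises when the results are mixed. If neither cytokine differed between groups but CRP did, the report could cite 5.1 and call CRP a primary result, or cite the Overview and call the primary outcome negative. Both would be faithful to the protocol. If the list is chosen after results are seen, a reader has no means of telling. In a trial of 40 patients, the main conclusion should not rest on which page is quoted.

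**Working it through.** **Step 1. The lists side by side.**

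| Marker | 5.1 primary list | 5.1 hypothesis | Overview hypothesis | Overview primary endpoints |
|---|---|---|---|---|
| IL-6 | yes | yes | yes | yes |
| TNF-α | yes | yes | yes | yes |
| S1P | yes | no | no | no |
| PCT | yes | no | no | no |
| CRP | yes | no | no | no |
| Leucocytes | yes | no | no | no |

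The disagreement is 6 − 2 = 4 markers. The 72-hour window appears in 5.1 and in the Overview's endpoint row; the Overview's hypothesis row gives no window. The two-item list occurs three times and the six-item list once, so the balance of the text favours IL-6 and TNF-α.

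**Step 2. Does the sample size settle it?** The sizing variable is IL-6 at 24 hours. IL-6 is on both lists, and 24 hours is one of the 5.1 time points and lies inside the 72-hour window. The sizing is compatible with either list and cannot choose between them.

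The plan's own figure was checked. Inputs from 5.3: difference 60 µg/L, SD 90 µg/L, 18 per group, 5% error, 90% power. The standardised difference is 60/90 = 0.667. A two-sided two-group comparison (noncentral t) then has 49.3% power, or 51.6% by the normal approximation, so the stated 90% is not reproduced. The drop-out step is: 18/0.9 = 20 per group. The power shortfall is a separate fault, and the conflict between the lists does not depend on it.

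**Step 3. What the decision rule does to the error rate.** The protocol does not say how many markers must succeed. Each test is taken at two-sided 5% with no true effect on any marker.

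- Both cytokines required: the chance that both are significant cannot exceed the chance that one is, so it is at most 5%. The same bound holds if only one cytokine is truly affected.
- IL-6 first, TNF-α only if IL-6 succeeds: at most 5%.
- Any one of two, independent: 1 − 0.95² = 9.75%.
- Any one of six, independent: 1 − 0.95⁶ = 26.5%.
- At an assumed between-marker correlation of 0.8, the last two fall to 7.8% and 13.9%.

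The last three lines illustrate a rule that the protocol does not contain.

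**Step 4. Price of requiring both cytokines.** If each test had 90% power and the two were independent, the chance that both succeed would be 0.9 × 0.9 = 81%. At the recomputed 49.3% it would be 0.493² = 24.3%, assuming the same standardised effect for TNF-α, for which the protocol gives no figures. Positive correlation between the tests would raise these values, up to the single-test power.

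**The case against.** The strongest reply is that the protocol already points to its own answer. IL-6 and TNF-α are on both lists and are the only markers in either statement of the hypothesis. An analysis plan confined to them would agree with everything except the 5.1 list, and an unseen plan may do exactly that. This stands as a guide to the fix. It does not remove the fault, because the 5.1 list would still label four further markers primary. This is a conflict between two statements in the protocol, not a detail left for later.

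Two stronger readings are tempting and are not supported.

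- A reader might infer a third primary definition from the sizing on IL-6 at 24 hours. Section 5.3 is a sizing assumption, not an endpoint definition, and powering a repeated-measures endpoint on one component at one time is ordinary practice. It contradicts neither list. The most that can be said is that the protocol does not explain how that comparison relates to the 72-hour endpoint.
- A reader might infer that the trial runs a false-positive risk of up to 26.5%. That needs a rule under which any single marker suffices. The protocol states none, and the hypothesis joins the two cytokines with *and*. Read plainly as both, the error stays at or below 5%.

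**Conclusion.** The contradiction is real and is in the current text. Four of the six markers called primary in 5.1 are not primary in the Overview or part of the hypothesis. A positive result on one of those four alone would concern a primary outcome under one list and not under the other. This conclusion rests on the wording alone and needs no assumption about effects, correlations or multiplicity.

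It does not show that the type I error is inflated, or that TNF-α must rank below IL-6. The error rates above 5% are illustrations under an unstated rule and, in part, assumed independence. The 90% power claim in 5.3 needs its own correction, which harmonising the endpoint does not supply.

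**What to change.** Before the cytokine data are analysed by group, amend the Protocol as follows.

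1. In 5.1, restrict the primary outcome to serum IL-6 and TNF-α, in line with the hypothesis and the Overview. Move S1P, PCT, CRP and leucocytes to the secondary outcomes, and show them as secondary in the Overview too.
2. State the decision rule. Suggested wording: *The primary claim requires a significant group difference in both IL-6 and TNF-α, each tested at two-sided 5%.* This follows the hypothesis as written and needs no split of the 5%. Testing IL-6 first, as the sized variable, and TNF-α only if IL-6 is significant is an acceptable alternative that also holds 5%.
3. In 5.1 and the Overview, say how the 72-hour endpoint relates to the 24-hour IL-6 comparison used for sizing in 5.3.

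The cost is an amendment. All six markers stay in the 5.8 schedule, so the change to the endpoint list needs no extra samples or visits. The downsides are that four markers lose primary status and that requiring both cytokines lowers the chance of a positive result. The alternative order avoids that loss for IL-6, but makes the TNF-α test conditional although the hypothesis names both cytokines equally.

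### Section 5.1 reads blood markers as organ function or inflammation while the adsorber runs in one arm only; for any marker the device itself removes, that reading is unsafe

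*Protocol*

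**What the plan says.** Section 4 presents the adsorber as "a device for effective elimination of cytokines like tumor necrosis factor" α, IL-6 and IL-8, and it also cites animal work on IL-10. These are the only substances the protocol names as removed.

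Section 5.1 states the comparison as cytokine levels "in patients undergoing hemoadsorption for 48 hours compared to a control group" on standard care. The primary parameters are "IL-6, TNF-a, S1P, PCT, CRP, leucozytes", introduced by the sentence "Laboratory parameters expressing an inflammatory response constitute the primary outcome of our study". They "are to be measured at time points 0,6,12,24,48 and 72 hours after administration to va-ECMO".

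The secondary parameters carry a different reading: "Those are supposed to reflect secondary and tertiary effects of the hemoadsorption on organ function and overall survival of the patients". The blood markers under that sentence are "NSE, (free) hemoglobine, haptoglobine, BNP, Troponine, Creatinekinase, Myoglobin, GOT, GPT, Creatinine". Section 5.8 repeats some of them as cardiocirculatory parameters ("BNP, Troponine, Creatinekinase, Myoglobine, Haptoglobine") and lists PCT as inflammatory. The study overview narrows the primary endpoints to IL-6 and TNF-α.

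The protocol does not say which of the listed markers the sorbent may bind. It does not separate removal by the device from reduced release, and it gives the 72-hour sample no special role.

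**The concern.** A serum concentration reflects both how much is released and how fast it is cleared. Reading a lower myoglobin as less organ damage, or a lower PCT as less inflammation, assumes that clearance is the same in both arms. Here the assigned treatment is a clearance device. For any marker it binds, clearance differs between the arms by design, so randomisation gives no protection. Where a lower value is read as better, as with myoglobin and PCT, the distortion favours the intervention arm.

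What is at stake is the organ-function conclusion, which section 3 names, with survival, as the ultimate aim. A lower value of an adsorbed marker would show that the filter works, yet section 5.1 would have it reported as an effect on the organ or on the inflammatory response. The cytokine hypothesis for IL-6 and TNF-α is not affected, because lowering those levels is the declared aim.

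**Working it through.** The protocol gives no figure on this point, so there is none to reproduce. The check has four parts.

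**1. Sampling against the run.** Inputs from section 5.1: the run lasts 48 h; samples are at 0, 6, 12, 24, 48 and 72 h. Assumption: the adsorber starts with va-ECMO (section 5.6 places randomisation at that moment, but no start time for the adsorber is given).
- During or at the end of the run: 6, 12, 24 and 48 h, so 4 of 5 post-baseline samples.
- After the run: 72 h only, 72 − 48 = 24 h after it ends. If the start is delayed by *d* hours, the gap shrinks to 24 − *d* hours.

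**2. What is read as what.**

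| Marker | Place in the protocol | Reading given | Named as removed in section 4? |
|---|---|---|---|
| IL-6, TNF-α | 5.1 primary; overview primary | the level itself is the target | yes |
| PCT | 5.1 primary; 5.8 inflammatory; not in the overview's primary endpoints | inflammatory response | no |
| Myoglobin | 5.1 secondary, one of ten blood markers; 5.8 cardiocirculatory | effect on organ function | no |

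The step from *some proteins are removed* to *this protein is removed* is therefore not in the protocol, for myoglobin or for PCT.

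**3. Size, if a marker is adsorbed.** Let *r* be device clearance divided by the patient's own clearance. The protocol gives no value, so *r* is an assumed range. With equal, constant release in both arms, level = release / (body clearance + device clearance). The ratio of intervention to control is then 1/(1 + *r*), and the fall is *r*/(1 + *r*).

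| *r* | ratio | fall with unchanged release |
|---|---|---|
| 0 (not adsorbed) | 1.00 | 0% |
| 0.10 | 0.91 | 9% |
| 0.50 | 0.67 | 33% |
| 1.00 | 0.50 | 50% |

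Steady state is doubtful after an acute insult. Take the opposite extreme: all release at time 0, one compartment, first-order elimination. After *m* body half-lives the ratio is 2^(−*rm*). With *r* = 0.5, the fall is 1 − 2^(−0.5) = 29% after one half-life and 1 − 2^(−1) = 50% after two. The size depends on the model. The direction does not.

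**4. Is the 72-hour sample clean?** Let *f* be the fall at 48 h and *k* the elimination rate once the adsorber is off, the same in both arms.
- If release continues at a constant rate, the remaining fall at 72 h is *f* · e^(−24*k*): smaller, but zero only in the limit.
- If release has ended by 48 h, both arms decline by the same factor e^(−24*k*), so the ratio at 72 h equals the ratio at 48 h. A 33% fall created by removal is still a 33% fall.

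The 72-hour value also exists only for patients alive at that time. It is less exposed than the earlier samples, but it is not free of the problem.

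**The case against.** The strongest objection is that the decisive premise is absent. The protocol credits the device with removing cytokines. It gives no molecular size, cut-off or statement of non-specific binding, and it does not say that myoglobin or PCT is bound. Zero bias fits the text as well as any other value. This stands, and it is why the point is conditional. A reader might infer that the myoglobin and PCT results will be biased, or that these two are the affected markers and creatine kinase is not. The documents support neither inference.

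A reader might also infer that a lower PCT would pass for organ protection. It would not: the sentence on organ function covers the secondary parameters only, and PCT is read as inflammatory response. The organ-function reading applies to myoglobin and to any other secondary blood marker that proves to be adsorbed.

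It is fair to say that no rule in the protocol makes a lower myoglobin proof of benefit. Echocardiography, haemodynamics, vasopressor need, organ replacement, length of stay and 30-day mortality are not serum concentrations and are not distorted in this way. That limits the reach of the point. It does not remove it, because section 5.1 itself states what the secondary parameters are meant to show. The classification is thus made in the protocol and not left to a later document.

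The steady-state model is only an illustration, as granted above. Nor should its output be set against the 20–30% difference in section 5.3. That figure concerns IL-6, where a lower level is the aim, and it is no benchmark for damage markers.

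**Conclusion.** The point holds in conditional form. For any listed blood marker that the adsorber clears, the reading in section 5.1 can turn removal into an apparent effect on organ function or inflammation. Where lower is read as better, the error favours the intervention arm. The illustrative size runs from 0% if the marker is not adsorbed to 50% if device clearance equals body clearance.

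This rests on two assumptions that the documents do not settle: that at least one listed non-cytokine marker is adsorbed, and that the adsorber starts at or near the start of va-ECMO. It would be tempting to treat the 72-hour sample as a clean test of damage, but carry-over and survivor-only sampling rule that out. The IL-6 and TNF-α hypothesis and the clinical outcomes are untouched.

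**What to change.** Before analysis, check every listed blood marker against the manufacturer's binding data and record the result. Then amend section 5.1 as follows:
- Class markers that are adsorbed as measures of removal by the device, and make no organ-damage or inflammation claim from them.
- Base organ-effect claims on listed markers shown not to be adsorbed and on the listed clinical outcomes: echocardiography, vasopressor need, organ replacement and 30-day mortality.
- Treat the 72-hour value of an adsorbed marker as supportive only, stating that earlier removal may carry over and that only survivors are sampled.

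The cost is a check of existing data and some protocol wording; no new samples or patients are needed. The downside is that any adsorbed marker loses its evidential role for organ effects. If the check finds none adsorbed beyond the cytokines, a sentence saying so closes the point.
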